7.2 Subject Discontinuation/Withdrawal from the Study

Subjects may be discontinued/withdrawn from the study for reasons that include, but are not limited to, the following:

- his/her own or parent/legal guardian request
- or he/she may be withdrawn at any time at the discretion of the Investigator for safety, behavioral, compliance, or administrative reasons (e.g., withdrawal of informed consent).

If the subject withdraws consent for disclosure of future information, the Sponsor may retain and continue to use any data collected before such a withdrawal of consent. If a subject withdraws from the study, he/she may request destruction of any samples taken and not tested, and the Investigator must document this in the study center study records. See [Table 1](#) and Table 13 for the data to be collected at the time of study discontinuation and follow-up and for any further evaluations that need to be completed. Subjects discontinued from the study at any time will be followed-up for additional 2 weeks for AEs.

The discontinuation of specific study centers or of the study are handled as detailed in [Appendix 1](#).

7.3 Lost to Follow-Up

A subject will be considered lost to follow-up if he/she fails to return for scheduled visits without notifying the site and the study center is unable to contact him/her as described below.

The following actions must be taken if a subject fails to return to the clinic for a required study visit:

- The study center must attempt to contact the subject and reschedule the missed visit as soon as possible and counsel the subject on the importance of maintaining the assigned

visit schedule and ascertain whether the subject wishes to and/or should continue in the study.

- Before a subject is deemed lost to follow-up, the Investigator or designee must make every effort to regain contact with the subject (where possible, 3 telephone calls and, if necessary, a certified letter to the subject's last known mailing address or local equivalent methods). These contact attempts should be documented in the subject's medical record.
- If the subject continues to be unreachable, he/she will be considered to have withdrawn from the study and lost to follow-up.

7.4 Pregnancy

Any female subject who becomes pregnant during the study must discontinue treatment. If a pregnancy is reported, the Investigator should inform the Sponsor within 24 hours of learning of the pregnancy and should follow the procedures outlined in [Section 8.4.3](#) and [Appendix 4](#).

8 STUDY ASSESSMENTS AND PROCEDURES

Study procedures and their timing for both the study and the Optional Maximal Use arm are summarized in the SoA ([Table 1](#) and [Table 13](#)). Adherence to the study design requirements, including those specified in the SoA, is essential and required for study conduct.

All screening evaluations must be completed and reviewed to confirm that potential subjects meet all eligibility criteria. The Investigator will maintain a screening log to record the details of all subjects screened and to confirm eligibility or record reasons for screening failure, as applicable.

Protocol waivers will not be considered for this study and assessments/procedures not completed as per protocol will be recorded as deviations. Acute safety concerns should be discussed with the Sponsor immediately upon occurrence or awareness to determine if the subject should continue or discontinue study treatment.

8.1 General Study Assessments

8.1.1 Informed Consent/Accent

A complete description of the study will be presented to the subject or parent/legal guardian of each potential subject (for subjects aged <18 years) and signed and dated. Informed consent will be obtained before any study-specific procedures are performed. The detailed informed consent process is described in [Appendix 1](#).

8.1.2 Genetic Testing

To be eligible for the study, subjects must have moderate to severe CI that has been genetically confirmed to be of either the ARCI or RXLI subtype. For ARCI subjects, enrollment is not limited to transglutaminase 1 mutations. Other genetically confirmed ARCI- mutations with a lamellar phenotype can potentially be enrolled ([Appendix 5](#)) as long as the phenotype is consistent with ARCI and the other inclusion criteria are met, as determined by the Investigator.

Genetic testing/confirmation will be performed at the time points designated in the SoA ([Table 1](#) and [Table 13](#)).

Subjects who already have had a genetic test documenting ARCI or RXLI types of CI will not be required to provide samples for genetic testing. However, the subject must provide the Investigator with a copy of the genetic report for the source documentation file.

Subjects requiring genetic test confirmation will have the testing performed by an independent laboratory after the Investigator or designee has determined they are likely to be otherwise eligible for enrollment. Genetic testing will consist of a buccal swab that is sent to one of two central laboratories depending on the subject's geographic location (North America vs Europe). The swab can either be obtained at the clinical site or by the subject at home. Instructions on how to complete the swab are included in the kit. The test will only report on genes associated with CI and results will be sent directly to the Investigator.

8.1.3 Demographics/Medical History

Medical history and demographic data including the subject's gender, date of birth, and concomitant medication use will be obtained for all subjects during Screening.

The medical history should be updated at Visit 2 (Baseline) prior to randomization (Phase III study) or first dose of study medication (Optional Maximal Use arm) to assess continued study eligibility and adherence to final inclusion/exclusion criteria. This medical history update includes a review for changes from Screening as well as a review of the patient's recent medication use to assess whether any changes have occurred since the previous visit.

8.2 Efficacy Assessments

Study procedures and their timing are summarized in the SoA ([Table 1](#)). Adherence to the study design requirements, including those specified in the SoA, is essential and required for study conduct.

8.2.1 Investigator's Global Assessment (IGA)

The primary efficacy assessment will be performed using the IGA (combined scaling and fissuring). For secondary efficacy assessments, scaling and fissuring will be evaluated separately using the respective sub-scores ([Table 9](#)).

Subject IGA scores will be assessed in the entire Treatment Area at the time points designated in the SoA ([Table 1](#)). The IGA score is a static evaluation of the overall or "average" degree of severity of a subject's disease, considering all the subject's scaling and/or fissuring in the Treatment Areas by the Investigator or designee. This evaluation takes into consideration the 2 individual characteristics of CI (scaling and fissuring) with the IGA score at each visit representing the average degree of scaling and/or fissuring. The IGA will be assessed using the 5-point scale as shown in Table 9. The same assessor should be evaluating the IGA scores at Baseline and throughout the study for each individual subject.

Table 9 Investigator's Global Assessment Score (5-Point Scale)

Score	Category	Scaling and Fissuring Combined Scores	Scaling Sub-score	Fissuring Sub-score
0	Clear	No scaling and no roughness, no fissuring	No scaling, no roughness	No fissuring
1	Almost Clear	Occasional fine scales, hardly palpable roughness (mostly smooth), rare fissuring and/or clinically insignificant fissuring severity	Occasional fine scales, hardly palpable roughness (mostly smooth)	Rare fissuring and/or clinically insignificant fissuring severity
2	Mild	Small and fine scales predominate, no more than a few large scales, mild roughness on palpation, few fissures with minimal pain or	Small and fine scales predominate, no more than a few large scales,	Few fissures with minimal pain or symptoms that impair patient ADLs and/or

Score	Category	Scaling and Fissuring Combined Scores	Scaling Sub-score	Fissuring Sub-score
		symptoms that impair patient ADLs and/or minimally clinically significant fissuring severity	mild roughness on palpation	minimally clinically significant fissuring severity
3	Moderate	Large rather thick scales predominate, coarse roughness on palpation, multiple fissures with possible pain or symptoms that somewhat impair ADLs and/or clinically significant fissuring severity	Large rather thick scales predominate, coarse roughness on palpation	Multiple fissures with possible pain or symptoms that somewhat impair ADLs and/or clinically significant fissuring severity
4	Severe	Large coalescent scales dominate, sharp edges on palpation with plate-like hyperkeratosis, numerous fissures and/or pain and symptoms that impair ADLs and/or very clinically significant fissuring severity	Large coalescent scales dominate, sharp edges on palpation with plate-like hyperkeratosis	Numerous fissures and/or pain and symptoms that impair ADLs and/or very clinically significant fissuring severity

IGA severity will be calculated as above using the scores obtained via one of the two methods below:

- On-site visual inspection
- Optional remote instead of on-site visits due to the ongoing Coronavirus Disease 2019 (COVID-19) pandemic comprised of both photographs and tele-medicine utilizing synchronous videoconferencing technology. The severity score at each visit will be based on information gathered from both sources to yield one score but remote evaluations cannot be used at Visits 1, 2, 6 or 9 unless there is a documented physical restriction to travel, such as COVID-19. All efforts will be made to have all visits on-site, the location of all assessments will be noted in the eCRF.

8.2.2 Visual Index for Ichthyosis Severity (VIIS) – Scaling

One of the key secondary efficacy assessments will be performed using the VIIS-scaling score. Subject VIIS-scaling scores will be assessed at the time points designated in the SoA ([Table 1](#)). Four VIIS Assessment Areas are defined as described below and will be further described using color illustrations in the Investigator Study Binder:

- (a) the upper back from the posterior axillary fold to the other encompassing the T1-T10,
- (b) the upper arm (excluding elbow), left or right,
- (c) the shin/lower leg (the portion below the proximal aspect of the kneecap), left or right
- (d) dorsal foot (left or right).

At least 2 of the 4 VIIS Assessment Areas MUST have a scaling score of 3 or more. The VIIS scores will be assessed using the 5-point scale as shown in Table 10.

Any VIIS Assessment Area that is graded initially as a 3 or 4 and will be treated is followed throughout the study for this secondary endpoint. Other VIIS areas should also be graded and may also be treated at the choice of the Investigator and subject but will not be used for the analysis of this endpoint.

One of the key secondary efficacy endpoints will be the proportion of subjects with VIIS "treatment success" (VIIS-50), which is defined as a 50% or greater decrease in VIIS-scaling score relative to Baseline at Visit 6 calculated using **only** the VIIS body areas described above that have a Baseline score ≥ 3 .

Table 10 Visual Index for Ichthyosis Severity Score (5-Point-Scale)

Score	Category	Description
0	Clear	normal skin with no smoothening or scales
1	Almost Clear	areas of normal skin intermixed with areas showing smoothening (diminished fine skin markings; shininess; waxiness) or small scales (visibly separated/fractured stratum corneum)
2	Mild	confluent smoothening (diminished fine skin markings; shininess; waxiness) or small scales (visibly separated/fractured stratum corneum)
3	Moderate	confluent scales (visibly separated/fractured stratum corneum) including some larger ($>1\text{cm}$), thick scales
4	Severe	confluent, primarily large ($>1\text{cm}$), thick scales

VIIS severity will be calculated as above using the scores obtained via one of two methods below:

- On-site visual inspection of the VIIS areas
- Optional remote instead of on-site visits due to the ongoing COVID-19 pandemic comprised of both photographs and tele-medicine utilizing synchronous video conferencing technology. The severity score at each visit will be based on information gathered from both sources to yield one score and remote data cannot be used at Visits 1, 2, 6 or 9 unless there is a documented physical restriction to travel, such as COVID-19. All efforts will be made to have on-site visits, the location of all assessments will be noted in the eCRF.

8.2.3 Defining Treatment Area and Percent Body Surface

The Treatment Area includes all affected skin where the study medication will be applied (**excluding** hands, face, neck, scalp, inner thighs and genitalia) and will be determined by Investigator and subject at Visit 1 (Screening). The percent BSA that the Treatment Area comprises will be recorded at Visit 1 (Screening) and used at randomization for determining the number of kits of study medication a subject will require for the study. The calculated percent BSA of the Treatment Area will be confirmed at Visit 2 (Baseline). The minimum affected area

to be treated will be no less than 10% and no more than 90% of the whole BSA at Visit 1 (Screening).

Note: The Treatment Area will remain the same throughout the study (unless treatment of a certain body part is discontinued due to persistent LSR).

8.2.4 Itch-Numeric Rating Scale (I-NRS)

Pruritus, from drug effect or allergic contact dermatitis, will be assessed with a self-administered electronic Patient-reported Outcome (ePRO) questionnaire using the I-NRS and WI-NRS daily through week 12. Subjects will indicate itch severity by selecting the severity level that best describes the worst level of itching due to CI in the past 24 hours on an 11-point scale anchored at 0 representing “no itching” and 10 representing “worst itch imaginable.” (see [Appendix 7](#)). Pruritus assessed by this evaluation should be reported as an AE only if therapy is required.

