2.3 Benefit/Risk Assessment

While no topical isotretinoin formulation is approved for use in treatment of CI (or any indication in the US), topical formulations of isotretinoin (e.g., 0.05% gel and 0.1% cream) have demonstrated some efficacy in reducing the clinical signs associated with ichthyosis and other disorders of keratinization. In one study, topical 13-cis-RA (isotretinoin) cream 0.1% demonstrated a marked reduction in scaling and an improvement in skin smoothness after 4 weeks of treatment in 40% of subjects (2/7 subjects with non-erythrodermic LI, 2/2 subjects with Darier's disease, and 0/1 subjects with autosomal dominant ichthyosis vulgaris). However, this clinical improvement was accompanied by local skin irritation (e.g., itchy erythema) in responders, and dose modifications were often prescribed to mitigate such effects ([Steijlen 1993](#)). Similarly, topical isotretinoin gel, 0.05% (Isotrex®) demonstrated partial resolution or clearance of hyperkeratosis and papules in the treatment area (10 cm² area) after 3 months of treatment (up to BID as tolerated) in 50% (6/12) of subjects with Darier's disease. In addition, systemic retinoids, including isotretinoin, have been used for the investigational treatment of CI and have demonstrated remarkable efficacy in reducing the clinical signs of the disease while dosing of the drug is maintained ([Vahlquist 2008](#), [Digiovanna 2013](#)).

The most notable adverse reactions with oral isotretinoin are: teratogenicity, dry lip, dry skin, back pain, dry eye, arthralgia, epistaxis, headache, nasopharyngitis, chapped lips, dermatitis, renal or hepatotoxicity, musculoskeletal discomfort, and visual acuity reduced.

The following are concerns for women of childbearing potential (WOCBP):

- Severe birth defects can occur during pregnancy while taking oral isotretinoin, with any amount and even if taken for short periods of time;
- Pregnancy must be avoided 1 month before, during, and for 1 month after treatment.

As with any retinoid, the side effects of TMB-001 may include the following LSRs: burning, dryness, edema, erythema, hyperpigmentation, hypopigmentation, photosensitivity, pruritus, scaling/peeling, stinging, and tenderness.

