8.4 Adverse Events

All AEs will be recorded. At each post-baseline visit, subjects will also be questioned specifically about the status of any ongoing AEs.

The definitions of an AE or SAE can be found in [Appendix 3](#).

AEs will be reported by the subject (or, when appropriate, by a caregiver, surrogate, or the subject's legally authorized representative).

Care will be taken not to introduce bias when detecting AEs and/or SAEs. Open-ended and non-leading verbal questioning of the subject is the preferred method to inquire about AE occurrences.

The Investigator and any designees are responsible for detecting, documenting, and recording events that meet the definition of an AE or SAE and remain responsible for following up AEs that are serious, considered related to the study medication or study procedures, or that caused the subject to discontinue the study. The trial blind may be broken for an individual only if knowledge of the investigational medicinal product is essential for clinical management of the subject.

8.4.1 Time Period and Frequency for Collecting Adverse Event and Serious Adverse Event Information

All AEs and SAEs will be collected from signing the ICF until the EOS visit at the time points specified in the SoA ([Table 1](#) and Table 13).

All SAEs will be recorded and reported to the Sponsor or designee within 24 hours, as indicated in [Appendix 3](#). The Investigator will submit any updated SAE data to the Sponsor within 24 hours of it being available.

After the initial AE/SAE report, the Investigator is required to proactively follow each subject at subsequent visits/contacts. All SAEs will be followed until resolution, stabilization, the event is

otherwise explained, or the subject is lost to follow-up (as defined in [Section 7.3](#)). Further information on follow-up procedures is given in [Appendix 3](#).

Investigators are not obligated to actively seek AE or SAE information after the conclusion of study participation. However, if the Investigator learns of any SAE, including a death, at any time after a subject has been discharged from the study, and he/she considers the event to be reasonably related to the study medication or study participation, the Investigator must promptly notify the Sponsor.

The methods of recording, evaluating, and assessing the causality of AEs and SAEs and the procedures for completing and transmitting SAE reports are provided in [Appendix 3](#).

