
• An AE is any untoward medical occurrence in a patient or subject, temporally associated with the use of study treatment, whether or not considered related to the study treatment.• NOTE: An AE can therefore be any unfavorable and unintended sign (including an abnormal laboratory finding), symptom, or disease (new or exacerbated) temporally associated with the use of study treatment.

Events Meeting the AE Definition

• Any abnormal laboratory test results (hematology, clinical chemistry, or urinalysis) or other safety assessments (e.g., ECG, radiological scans, vital signs measurements), including those that worsen from Baseline, considered clinically significant in the medical and scientific judgment of the Investigator (i.e., not related to progression of underlying disease).• Exacerbation of a chronic or intermittent pre-existing condition including either an increase in frequency and/or intensity of the condition, including local skin reactions.• New conditions detected or diagnosed after study treatment administration even though it may have been present before the start of the study.• Signs, symptoms, or the clinical sequelae of a suspected drug-drug interaction.• Signs, symptoms, or the clinical sequelae of a suspected overdose of either study treatment or a concomitant medication. Overdose per se will not be reported as an AE/SAE unless it is an intentional overdose taken with possible suicidal/self-harming intent. Such overdoses should be reported regardless of sequelae.• "Lack of efficacy" or "failure of expected pharmacological action" per se will not be reported as an AE or SAE. Such instances will be captured in the efficacy assessments. However, the signs, symptoms, and/or clinical sequelae resulting from lack of efficacy will be reported as AE or SAE if they fulfil the definition of an AE or SAE.

Events NOT Meeting the AE Definition

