5.2.2 Analysis Methods

Statistical testing will be performed on the key secondary efficacy endpoints using a two-side alpha of 0.01, according to the following hierarchical order.

5.2.2.1 IGA Clear Score Responders at Week 12

The difference in proportions of subjects with IGA score of clear or almost clear (henceforth referred to as 'IGA clear score responders') versus mild/moderate/severe will be computed at Week 12, between the TMB-001 0.05% and vehicle treatment groups.

The difference in proportions will be calculated in a similar manner as the primary efficacy endpoint using the CMH test, including the use of 50 multiply imputed datasets combined using the Wilson-Hilferty transformation for the pooled CMH statistic and Mantel-Haenszel stratum-weighted difference in proportions combined using Rubin's rule. Results will be provided using the primary efficacy data presentation.

5.2.2.2 IGA-Scaling Sub-Score Responders at Week 12

The difference in proportions of subjects with a ≥ 2 point change from baseline in IGA-scaling severity sub-scores (henceforth referred to as 'IGA-scaling sub-score responders') will be computed at Week 12 among subjects who have a score of ≥ 3 at baseline, between the TMB-001 0.05% and vehicle treatment groups.

The difference in proportions will be calculated in a similar manner as the primary efficacy endpoint using the CMH test, including the use of 50 multiply imputed datasets combined using the Wilson-Hilferty transformation for the pooled CMH statistic and Mantel-Haenszel stratum-weighted difference in proportions combined using Rubin's rule. Results will be provided using the primary efficacy data presentation.

5.2.2.3 Worst Itch-QoL (WI-NRS) Responders at Week 12

The difference in proportions of subjects achieving a ≥ 4 -point improvement from baseline in weekly Worst Itch-QoL scores on the WI-NRS (henceforth referred to as 'Worst Itch-QoL (WI-NRS) responders') will be computed at Week 12, between the TMB-001 0.05% and vehicle treatment groups. Only subjects with baseline WI-NRS scores of ≥ 7 will be included in this analysis.

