7.2.1 Local Skin Reactions

The incidences of local skin reactions (LSRs) will be summarized for all visits according to the skin irritation scale (Grade 0 – none, Grade 1 – mild, Grade 2 – moderate, Grade 3 – severe) and type of reaction (burning/stinging, erythema, erosions, and edema). Changes from baseline will also be summarized for all visits and will be categorized into

'worsened' and 'same or improved' categories. For subjects reporting more than one occurrence of the same type of reaction, the most severe reaction will be used for the summary.

The proportion of subjects experiencing a LSR through Week 12 will be reported along with exact binomial 95% confidence intervals, using the primary safety data presentation. The proportion of subjects experiencing a LSR through Week 24 will be reported along with exact binomial 95% confidence intervals, using the open-label dosing data presentation. Additionally, the Week 12 analysis will be repeated, separating subjects that had ≥ 10 Cetaphil applications within the first 21 days, versus subjects that had < 10 Cetaphil applications.

Additionally, the number and percentage of subjects who had suspected allergic contact dermatitis will be provided for all visits, along with exact binomial 95% confidence intervals. The number of subjects with confirmed cases of allergic contact dermatitis will be reported as well; subjects with confirmed cases are defined as those who had a suspected event reported, **and** allergic contact dermatitis reported as an AE.

A by-subject listing will be provided for all local skin reaction data.

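### Itch captured on the itch scale becomes an AE only if treated, and no planned analysis counts new or worsened itch, so drug-induced itch may be under-ascertained

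*Protocol*

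**What the plan says.** **AE rule.** Protocol 8.2.4 opens: "Pruritus, from drug effect or allergic contact dermatitis, will be assessed with a self-administered electronic Patient-reported Outcome (ePRO) questionnaire". The subject, however, is to rate the "worst level of itching due to CI in the past 24 hours", and the items printed in Appendix 7 ask about average and worst itch with no cause named. Section 8.2.4 then closes with the rule: "Pruritus assessed by this evaluation should be reported as an AE only if therapy is required".

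**General AE rules.** Protocol 8.4 states: "All AEs will be recorded". Appendix 3, among events meeting the AE definition, includes: "Exacerbation of a chronic or intermittent pre-existing condition including either an increase in frequency and/or intensity of the condition, including local skin reactions". Its list of events that are not AEs exempts symptoms of the disease under study, unless they are more severe than expected for the subject. Neither list mentions therapy.

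**Expected reactions.** Protocol 2.3 introduces its list with "As with any retinoid, the side effects of TMB-001 may include the following LSRs", and pruritus is on that list. Protocol 8.3.3 names burning/stinging, erythema, erosions and edema for grading, with a loose reference to other causes. Protocol 10.3.1.3.4 summarises the same four plus unspecified others. SAP 7.2.1 keeps only the four: "type of reaction (burning/stinging, erythema, erosions, and edema").

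**Itch analyses.** For the Week 12 key secondary endpoint, SAP 5.2.2.3 restricts entry: "Only subjects with baseline WI-NRS scores of" 7 or more are included. SAP 5.4.3 does the same at Week 24. Addendum 2.0 adds versions with baseline 4 or more, chosen so that a 4-point reduction is possible. SAP 5.1 plans descriptive tables of efficacy measurements over time, and SAP 5.2.2.3 and 5.4.3 plan a descriptive I-NRS analysis where applicable.

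**The concern.** Itch can move in either direction in this trial. It is a symptom of congenital ichthyosis that TMB-001 may relieve, and a retinoid reaction that TMB-001 may cause. The plan gives the first direction an alpha-controlled endpoint. The second depends on AE reporting, and for itch seen on the scale that reporting carries a therapy condition which the general AE definition lacks.

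Several listed reactions (dryness and pigment change, for example) are also not graded, but only pruritus carries this extra condition. A subject whose worst itch rises from 1 to 6 and who receives no therapy need not appear as an AE under 8.2.4, has no named LSR grade, and is outside every responder analysis.

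At stake are the pruritus rate in the TEAE tables, possibly its place among common TEAEs (5% or more in either group, Protocol 10.3.1.2), and the balance of any itch-benefit statement. The primary endpoint is not affected.

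**Working it through.** The plan states no figure on this point, so the check sets the rules side by side and then illustrates scale under stated assumptions.

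**Step 1. Is there a conflict on AE capture?**

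| Source | When is new or worse itch an AE? | Therapy needed? |
|---|---|---|
| Protocol 8.2.4 | when captured on the itch scale | yes |
| Protocol 8.4 | whenever it is an AE | no |
| Appendix 3, events meeting the definition | worsening in frequency or intensity of a pre-existing condition, LSRs included | no |
| Appendix 3, events not meeting it | disease symptom, only if more severe than expected | no |

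Untreated itch that has clearly worsened is an AE under Appendix 3 and not one under 8.2.4. The conflict is real.

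**Step 2. How wide is the therapy trigger?** After Week 3, Protocol 6.5 reserves emollient and low-potency hydrocortisone for severe discomfort (itch is an example) that interruption alone is judged unable to relieve. Protocol 7.1 leaves similar treatments to investigator discretion. The two must be reconciled; until then the share of itch that meets the trigger is undefined. Section 8.2.4 does not say whether a dose interruption counts as therapy.

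**Step 3. Does another analysis pick it up?** The LSR tables name four types without itch. The responder analyses count decreases of at least 4 points above a baseline threshold. The descriptive tables give means, medians, SDs and ranges by arm (SAP 3.2.1). They may include low-baseline subjects, but an arm-level average can hide individual worsening behind improvement in others. The I-NRS analysis concerns average itch, not worst itch (Appendix 7). None counts subjects who worsen.

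**Step 4. Scale, by illustration.** Assumed, not from the documents: true new or worse itch 30% on TMB-001 and 10% on vehicle, with the same treated share f in both arms. Arm sizes: 110 × 2/3 ≈ 73 and 110 × 1/3 ≈ 37. Recorded rate = true rate × f. With 73 subjects, reaching 5% takes at least 4 (4/73 = 5.5%; 3/73 = 4.1%); the last column is the binomial probability of that.

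| f | TMB-001 | Vehicle | Difference | Ratio | P(TMB-001 arm reaches 5%) |
|---|---|---|---|---|---|
| 1 | 30% | 10% | 20 points | 3 | about 100% |
| 0.5 | 15% | 5% | 10 points | 3 | about 100% |
| 0.25 | 7.5% | 2.5% | 5 points | 3 | 81% |
| 0.1 | 3% | 1% | 2 points | 3 | 18% |

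With equal f the ratio stays at 3, while the absolute rates and the difference shrink in proportion to f.

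**Step 5. Can the existing data show worsening?** Yes. Protocol 8.2.4 collects I-NRS and WI-NRS daily in both arms through Week 12, and SAP 5.2.2.3 already defines weekly averages mapped to visits. On a 0 to 10 scale a 4-point increase requires a baseline of at most 10 − 4 = 6. Early subjects have a single baseline score rather than a weekly average.

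**The case against.** The strongest defence is that pruritus is a feature of the disease (Protocol 2) and the scale is filled in daily. Appendix 3 excludes expected disease symptoms and day-to-day fluctuation that does not worsen, so some rule separating diary noise from AEs is reasonable. That stands. It does not justify a therapy test, because Appendix 3 separates the two by severity relative to expectation, and 8.2.4 itself names drug effect as a source of the itch.

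Four stronger readings might be inferred, and the documents do not support them:

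- **That itch is analysed only in subjects who start itchy.** SAP 5.1 plans descriptive tables of all efficacy measurements. The limit to subjects eligible to respond most naturally attaches to the line plots, and the descriptive I-NRS analysis states no baseline threshold.
- **That every other safety route is closed.** The 8.2.4 rule covers itch assessed by that scale. Whether itch volunteered at open AE questioning (8.4) falls under it is not stated. Protocol 8.3.3 and 10.3.1.3.4 leave room for other LSRs, and the overall LSR proportion in SAP 7.2.1 is not expressly limited to the four types.
- **That drug itch is under-reported by a known amount, or that TMB-001 is favoured.** No pruritus rate or treated share is given, and the rule applies to both arms. Safety endpoint 8b counts subjects with any TEAE, so a subject with another event is already included; its loss is smaller than that for pruritus alone, by an unknown amount.
- **That most subjects fall outside the WI-NRS analyses.** Addendum 2.0 says the number with baseline 7 or more was unexpectedly low, but gives no count there or below 4.

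**Conclusion.** The concern holds as a risk of under-ascertainment. Protocol 8.2.4 conflicts with 8.4 and Appendix 3 on when itch is an AE. The documents disagree on whether pruritus belongs among the reported LSRs. No specified analysis counts new or worsened itch, although improvement is tested under alpha control. Following the plan as written can leave untreated drug-induced itch out of the TEAE tables.

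The amount cannot be stated. Step 4 shows only the mechanism: absolute rates and the difference scale with the treated share, and the ratio is unchanged if that share is equal across arms. If the share differs by arm, the ratio moves too, in a direction the documents do not allow one to predict. The change is worth making because the data exist and the safety description of an expected reaction depends on it.

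**What to change.** 1. **Protocol 8.2.4.** Reconcile it with 8.4 and both lists in Appendix 3, so that AE reporting of new or worsened itch follows the Appendix 3 definition. Say whether itch volunteered at AE questioning is handled the same way.
2. **LSR lists.** Reconcile Protocol 2.3, 8.3.3 and 10.3.1.3.4 with SAP 7.2.1 on whether pruritus is a reported LSR.
3. **SAP 7.2.1.** Add a by-arm table for Phase III Safety subjects, regardless of the baseline 7 or 4 threshold: number and percentage with an increase of at least 4 points from baseline in weekly WI-NRS at any visit through Week 12. Show it also for subjects with baseline 6 or less, who are able to score such an increase, and flag those with a single-day baseline, where the change is noisier. Restrict it to Phase III subjects, because the SAP's Safety population includes the Maximal Use arm.
4. **SAP 5.1.** State whether the limit to subjects eligible to respond applies to the descriptive tables or only to the plots.

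The cost is one reworded protocol section, one extra table, more AE entries and a less favourable AE profile. The table cannot separate drug itch from disease flare within a subject; the vehicle arm supplies that comparison. If enrolment is over, rewording 8.2.4 does little for events already collected. The table needs no new data and can still be added, identified as an addition.
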